5.7.2 Fluid and Food Intake

An overnight fast of at least 10 hours prior to dosing is required. Study drug(s) will be taken in the morning with approximately 240 mL of water prior to any drinking or eating. Water is permitted during the fasting period up to 1 hour before and after the administration of each study drug administration. Adequate hydration is encouraged during the study period. Food can be consumed 4 h after dosing.

5.7.3 Subject Activity Restrictions

Light physical activity is permitted. Subjects should not perform strenuous activity which could result in elevations of muscle creatine kinase levels within 72 h prior to first dose and through the end of the study. Smoking during the study is prohibited. Alcohol consumption is restricted for 24 hours prior to each clinic admission check-in. Subjects must refrain from smoking, or consuming alcohol, grapefruit, grapefruit juice or related products, or caffeine (including chocolate), during the duration of the study.

5.8 Treatment Compliance

To ensure compliance, all medication dosing will be supervised by the Investigator or qualified staff in the clinic. The exact times of medication dosing will be recorded in the CRFs, including a record of checks followed by hand mouth inspection.

5.9 Packaging and Labeling

5.9.1 Bexagliflozin

Bexagliflozin tablets, 20 mg, are packaged in high density polyethylene bottles sealed with a child resistant closure. The product is packaged with 90 tablets per bottle. Investigational product bottles will be labeled with protocol number, drug name and strength, lot number, sponsor's name, storage condition, and the investigational drug caution statement.

5.9.2 Digoxin

Digoxin tablets are packaged with 100 tablets per bottle. Digoxin bottles are labeled with drug name, strength, lot number, expiration date, storage and dispensation information and drug caution statement.

5.10 Storage and Accountability

All drug supplies should be stored in a secure area with access limited to authorized personnel. Bexagliflozin tablets should be stored below 30°C. Digoxin should be stored at 15° to 25°C in a dry place and protected from light, and dispensed according to label instructions. The sponsor will perform an ongoing inventory of study products. The responsible pharmacist must keep a careful inventory of drug shipments received and the number of tablets dispensed per study subject. A full reconciliation of drug inventory will be performed at the end of the study and the results of this inventory must be recorded in the Clinical Trial Material Inventory Logs and Accountability Logs. At study close out after the post-study inventory reconciliation is completed, empty and partially used bottles of bexagliflozin tablets will be returned to the originating IP depot for destruction. Digoxin bottles may be discarded according to the study sites' regulations for the disposal of investigational drug products.

6 STUDY PROCEDURES

6.1 Informed Consent

Before each subject is enrolled in the clinical study, written informed consent will be obtained from the subjects according to the regulatory and legal requirements. As part of this procedure, the investigator or designee must explain orally and in writing the nature, duration, and purpose of the study, and the action of the drug in such a manner that the study subject is aware of the potential risks, inconveniences, or AEs that may occur. The investigator should educate potential subjects about the scientific importance of their data and the vital role that their participation has for the outcome of the entire study. The subject must be informed that he/she is free to withdraw from the study at any time. He/she will receive all information that is required by federal regulations and International Council for Harmonisation (ICH) guidelines.

The informed consent document must be signed and dated. One copy will be given to the subjects, and the investigator will retain a copy as part of the clinical study records. The investigator will not undertake any investigation specifically required for the clinical study until written consent has been obtained. The terms of the consent and when it was obtained must also be documented.

6.2 Medical History

The following information will be collected at the screening visit:

- Demographic information including age, sex, and race.
- Significant medical, surgical history (i.e. cholecystectomy, kidney transplant, etc.) and timeframe of the history relative to study screening, if applicable.
- Clinically significant history of allergy including drugs and latex.
- History of smoking in the last 6 months prior to first dose, and alcohol or drug dependence, or abuse in the last 12 months prior to first dose.
- Any blood donation within 56 days or blood component donation in the last 14 days prior to first dose.
- Use of any medications including OTC drugs or dietary supplements in the last 14 days prior to first dose. Use of any vitamins in the last 7 days prior to first dose.
- History of vaccination (except the flu vaccine) within 30 days prior to first dose.
- History of diagnosis with HIV, hepatitis B or hepatitis C.
- Use of any investigational drug in the previous 30 days or 7 half-lives prior to first dose, whichever time frame is longer.
- Prior exposure to bexagliflozin (or EGT0001474), or any other SGLT2 inhibitors in the last 3 months prior to first dose.
- Prior exposure to digoxin in the last 3 months prior to first dose.
- History of recurrent yeast or urinary tract infections or any such infections in the last 6 months prior to first dose.

6.3 Physical Examination

The investigator or designated qualified individual will perform the PEs. A complete PE will be performed at screening and on the last day of Period 2 prior to discharge. Partial PEs will be performed on scheduled days as described in [Appendix 1](#).

A complete PE will include measurement of body weight and height (height will be measured only at screening), general assessment of all body systems including the skin, head, eyes, ears, nose, throat, neck, lungs, heart, abdomen, lymph nodes, and extremities. A partial PE will include body weight and an update of the general assessment of the skin, heart, lungs and abdomen.

6.4 Vital Signs

Vitals signs, including pulse, systolic and diastolic blood pressure (BP), respiration rate, and oral temperature, will be measured on scheduled visits as described in [Appendix 1](#).

Vital signs should be measured prior to blood draws.

Pulse, systolic and diastolic BP should be measured in a seated position after a subject has been sitting for 5 minutes.

Respiration rate should be measured after at least 5 minutes of rest.

BP measures will be obtained using a calibrated sphygmomanometer or calibrated automated vitals machine.

6.5 Electrocardiography

A 12-lead electrocardiography (ECG) will be conducted as listed in [Appendix 1](#) and whenever clinically indicated.

This procedure should be performed in the supine position after at least 5 minutes of rest. ECG parameters measured will be the RR interval, PR interval, QRS duration, and QT. Each ECG should also be assessed by the investigator for signs of ischemia, clinically significant hypertrophy, and clinically significant T-wave abnormalities.

It is the investigator or designee's responsibility to review the results of the ECG as they become available. For each abnormal ECG result, the investigator needs to ascertain if this is a clinically significant change from the screening ECG for that individual subject. This determination, however, does not necessarily need to be made the first time an abnormal result is observed. The investigator may repeat the ECG to verify the results of the original result. If the ECG result is determined to be a clinically significant and an abnormal change from baseline for that subject, this is considered an AE.

6.6 Clinical Laboratory Tests

6.6.1 Laboratory Parameters

Subjects will be in a seated, semi-recumbent or in a supine position during blood collection. Clinical blood chemistry and hematology tests will be performed at the scheduled visits ([Appendix 1](#)). Blood samples should be drawn after overnight fasting prior to breakfast. The details of the required laboratory tests are listed in Table 1.

Table 1. Required Laboratory Tests

Test Name	mL (sample)
Hematology	4.0 (blood)
Hematocrit	Mean corpuscular volume
Hemoglobin	Platelet count
Mean corpuscular hemoglobin	Red blood cell count
Mean corpuscular hemoglobin concentration	White blood cell count with differential
Serum Chemistry, Electrolytes and Lipids	8.5 (serum)
Albumin	Calcium
Alanine aminotransferase (ALT)	Magnesium
Aspartate aminotransferase (AST)	Phosphorus
Blood urea nitrogen (BUN)	Potassium
Glucose	Sodium
Total Carbon Dioxide	Total bilirubin
Creatinine	Direct bilirubin
Chloride	Uric acid
Total protein	Total cholesterol
Low-density lipoprotein cholesterol, calculated	High-density lipoprotein cholesterol
Triglycerides	
Urinalysis	20 (urine)
Appearance	Nitrite
Bilirubin	pH
Color	Protein
Glucose	Specific gravity
Ketones	Urobilinogen
Microscopic examination of sediment	Leukocyte esterase
Urine Drug Screen	10 (urine)
Amphetamines	Opiates
Barbiturates	Benzodiazepines
Cocaine Metabolites	Cannabinoids
Cotinine	
Urine Pregnancy Test (Female only)	5 (urine)
Infectious Disease Testing	3.5 (serum)
Hepatitis B surface antigen (HBsAg)	Hepatitis C virus (HCV)

6.6.2 Sample Collection, Storage, and Shipping

6.6.2.1 Hematology and Blood Chemistry

Blood samples for hematology and chemistry will be collected. Timing of the collection is described in [Appendix 1](#).

6.6.2.2 Urinalysis

Clean-catch, midstream urine samples will be collected per schedule outlined in [Section 7](#) and in [Appendix 1](#). Dipstick urinalysis will be conducted. Microscopy will be obtained if the subject has a positive result on any of the dipstick tests that require microscopic follow-up to clarify their significance. If urine is dipstick positive for white blood cell (count) (WBC) or blood (except female subjects who are menstruating), urine sample will be sent for microscopic evaluation and culture. In addition, urinalysis will be performed from a clean-catch urine sample at any time in subjects with symptoms of UTI or pyelonephritis.

6.6.2.3 PK Plasma Sample Collection and Analysis

Whole venous blood samples of 3 mL will be collected from a peripheral vein in each period at pre-dose and at 0.5, 1, 1.5, 2, 3, 4, 6, 8, 12, 24, 48, 72, 96, and 120 h post-dose of digoxin for Groups 1 and 2. Blood samples will be collected in tubes containing potassium ethylenediaminetetraacetic acid (K₂EDTA) and stored on ice until centrifuged under refrigeration for at least 5 min at 3,000 rpm. After centrifugation, plasma will be removed, divided into 2 aliquots of approximately 0.5 mL, frozen and stored at or below -20°C. Plasma should be processed and frozen within 2 h of blood collection. Processed frozen plasma samples will be transferred on dry ice to the analytical laboratory and will be stored at or below -20°C until analysis.

Plasma concentrations of digoxin will be determined at Covance by validated liquid chromatography - mass spectrometry (LC-MS/MS) method, with lower limit of quantitation (LLOQ) of 0.05 ng/mL for digoxin.

6.7 Adverse Events Assessments

Adverse Event (AE): Any untoward medical occurrence in clinical investigation subject administered a pharmaceutical product. An AE does not necessarily have to have a causal relationship with this treatment.

An AE can therefore be any unfavorable and unintended sign (including an abnormal laboratory finding, for example), symptom, or disease temporally associated with the use of an investigational product, whether or not it is considered related to the investigational product.

Serious Adverse Event (SAE): A serious adverse event (experience) or reaction is any untoward medical occurrence that at any dose:

- results in death,
- is life-threatening (*NOTE: The term "life-threatening" in the definition of "serious" refers to an event in which the patient was at risk of death at the time of the event and does not refer to an event which hypothetically might have caused death if it were more severe.*),
- requires inpatient hospitalization or prolongation of existing hospitalization,
- results in persistent or significant disability/incapacity,
- is a congenital anomaly/birth defect,
- is an important medical event.

An important medical event is an event that may not be immediately life-threatening or result in death or hospitalization but may jeopardize the patient or may require intervention to prevent one of the other outcomes listed in the definition above. Examples of such events are intensive treatment in an emergency room or at home for allergic bronchospasm, blood dyscrasias or convulsions that do not result in hospitalization, or development of drug dependency or drug abuse.

Non-serious adverse events are all events that do not meet the criteria for a "serious" adverse event.

Immediately Reportable Adverse Event (IRAE): Any serious adverse event or any adverse event that necessitates discontinuation of investigational product.

Clinical Laboratory Changes: It is the investigator's responsibility to review the results of all laboratory tests as they become available. For each abnormal laboratory test result, the investigator needs to ascertain if this is a clinically significant change from baseline for that individual subject. This determination, however, does not necessarily need to be made the first time an abnormal value is observed. The investigator may repeat the laboratory test or request additional tests to verify the results of the original laboratory tests. If this laboratory value is determined to be a clinically significant change from baseline for that subject, this is considered an AE.

Hypoglycemia will be defined as any fasting plasma glucose (FPG) value < 70 mg/dL and documented as described in [Section 6.7.4.4](#).

Any increase in liver function tests (aspartate aminotransferase (AST), alanine aminotransferase (ALT), or bilirubin) greater than 3 times the upper limit of normal (ULN) for the laboratory utilized will be considered a clinical laboratory adverse event.

An increase in creatinine from baseline by 0.5 mg/dL or more will be reported as a laboratory adverse event.

Severity: Adverse events will be graded on a 3-point scale and reported as indicated on the CRF. The intensity of an adverse experience is defined as follows:

1 = Mild: discomfort noticed, but no disruption to daily activity

2 = Moderate: discomfort sufficient to reduce or affect normal daily activity

3 = Severe: inability to work or perform normal daily activity

Investigational Product Causality: The site and database should ask for the causality relative to the study compound. Relationship of an adverse event to dosing will be assessed as follows:

Definite: There is a reasonable causal relationship between the investigational product and the AE when the event responds to withdrawal of the investigational product (dechallenge), and recurs with administration of the investigational product (rechallenge).

Probable: There is a reasonable causal relationship between the investigational product and the AE. The event responds to dechallenge. Rechallenge is not required.

Possible: There is a reasonable causal relationship between the investigational product and the AE. Dechallenge is lacking or unclear.

Not Likely: There is a temporal relationship to investigational product administration, but there is not a reasonable causal relationship between the investigational product and the event.

Unrelated: There is no temporal or causal relationship to investigational product administration.

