5 STUDY TREATMENT(S)

5.1 Description of Treatment(s)

5.1.1 Investigational Product: Bexagliflozin

Bexagliflozin tablets, 20 mg, are blue caplet-shaped, film-coated tablets that are intended for use in investigational studies in humans. The tablets contain excipients designed to promote extended release through a gastroretentive mechanism. The active tablets exhibit a greater than 75% release of drug substance by 8 hours in simulated gastric fluid *in vitro*.

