5.1.2 Cardiovascular Drug: Digoxin

Digoxin is a cardiac glycoside that mediates its effects on Na/K ATPase to increase cardiac output. Majority of digoxin is excreted in urine and bile unchanged, and metabolism of digoxin appears to be minimal (Iisalo, 1977). After oral administration, the absorption of digoxin is mediated by P-glycoprotein (P-gp). 0.25 mg digoxin tablets are white, round tablets with an imprint code JSP-545. 0.25 mg digoxin tablets are the highest available tablet dose, and two 0.25 mg tablets will be taken q.d. for this study.

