9.6.1 Adverse Events

Adverse events will be mapped to preferred term and body system using the Medical Dictionary for Regulatory Activities (MedDRA). The number and percentage of subjects reporting adverse events will be determined by relationship to treatment and by severity of the event. Drug-related adverse events will be considered those to be possibly related to bexagliflozin administration.

Adverse event listings will be provided for the following subsets:

- all treatment emergent AEs (TEAEs).
- all TEAEs at least possibly related to bexagliflozin.
- serious TEAEs (if any).
- TEAEs leading to study discontinuation (if any).

AEs are dosing emergent if they occur on or after bexagliflozin administration. TEAEs will be considered at least possibly related to bexagliflozin based on the investigator's assessment. Only TEAEs will be tabulated in summary tables. If the AE(s) onset date-time or date occurs after the first dose up until right before the next dose, the AE(s) will be assigned

to the first treatment. Any AE(s) that occur after the second dose up until the follow-up visit will be assigned to the second treatment.

Tabulations will display TEAEs by severity and relationship to bexagliflozin.

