2.2 Secondary Objectives

The secondary objective of this study is to evaluate the safety and tolerability of digoxin when co-administered with bexagliflozin.

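### The Protocol judges adverse-event relatedness against bexagliflozin only, so a digoxin reaction on digoxin alone has little or no route to being counted as drug-related

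*Protocol*

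**What the plan says.** Protocol 6.7, under investigational product causality, gives one instruction: "The site and database should ask for the causality relative to the study compound". The five grades that follow all refer to the investigational product. The lowest, Unrelated, reads "There is no temporal or causal relationship to investigational product administration". The treatment descriptions are headed "5.1.1 Investigational Product: Bexagliflozin" and "5.1.2 Cardiovascular Drug: Digoxin", so only bexagliflozin carries the investigational label there.

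Protocol 9.6.1 applies this to the analysis: "Drug-related adverse events will be considered those to be possibly related to bexagliflozin administration", and "Tabulations will display TEAEs by severity and relationship to bexagliflozin". The listing of related events is also defined by bexagliflozin. The same section says "AEs are dosing emergent if they occur on or after bexagliflozin administration".

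The SAP is less definite. Section 6.3.3 has investigators assess relationship to *study drug*, and Section 5.1 uses *either study drug* to cover both products. Section 6.3.3.1 counts an event as treatment-emergent after either drug. But Section 6.3.3.6 is headed by the investigational medicinal product and takes its criteria from the Protocol, citing Section 6.9 (subject removal) when they stand in 6.7. The SAP objective is: "The secondary objective of this study is to evaluate the safety and tolerability of digoxin when co-administered with bexagliflozin".

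**The concern.** The objective is about digoxin, but the Protocol's relatedness judgement is about the other drug. The same digoxin reaction can be graded Possible while the subject takes bexagliflozin daily, yet has little or no route to that grade on digoxin alone. Related status would then partly mark which treatment the subject was on rather than what caused the event.

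Two things are at stake. A display of related events by treatment could show an excess on the combination when bexagliflozin adds nothing. And a digoxin reaction that an investigator correctly judges unrelated to bexagliflozin would not be identified as drug-related under either treatment. The Protocol introduction itself stresses digoxin's narrow therapeutic index, so these reactions are the ones a reader will look for.

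**Working it through.** The plan gives no figure to reproduce. It states no adverse-event rates, SAP 3.5 gives the sample size no formal basis, and SAP 3.3 plans no hypothesis test. The check is a reading of the rules, one interval calculation and one illustration.

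**1. What the grades allow.** Definite, Probable and Possible each need a reasonable causal link to the investigational product. Not Likely needs a temporal link to it. Unrelated needs neither. With Sections 5.1.1, 5.1.2 and 9.6.1, the reference drug in the Protocol is bexagliflozin.

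**2. Bexagliflozin exposure before each digoxin-alone dose** (days from Protocol Appendix 2, half-life 7.80 to 9.71 h from Protocol 3.2.3).

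- Group 2 Period 1: digoxin on Day 1, first bexagliflozin on Day 15. Earlier bexagliflozin doses in the study: 0. Only Unrelated is available.
- Group 1 Period 2: last bexagliflozin on Day 8, digoxin on Day 19. Interval = (19 − 8) × 24 = 264 h. In half-lives: 264 / 9.71 = 27.2 and 264 / 7.80 = 33.8. Attribution to bexagliflozin is implausible, but the grades set no time window that forbids it.

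The strict exclusion therefore covers about 9 of the 18 planned digoxin-alone subject-periods.

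**3. Illustration of size.** Let *p* be the probability that digoxin causes an event in a subject-period, the same under both treatments. Let *q* be the share of those events attributed to bexagliflozin on Treatment A. Both are assumptions: *p* = 0.10 to 0.30, *q* = 0.5 to 1.0. With N = 18 per treatment:

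- Expected related subjects on A = N × *p* × *q*. Low end: 18 × 0.10 × 0.5 = 0.9. High end: 18 × 0.30 × 1.0 = 5.4.
- Chance of at least one on A = 1 − (1 − *pq*)^18. Low end: 1 − 0.95^18 = 0.60. High end: 1 − 0.70^18 = 0.998.
- Expected on B: about 0, taking it that no event in Group 1 Period 2 is attributed to bexagliflozin and no relationship is missing.
- Artificial gap = *pq* = 5 to 30 percentage points, with a true difference of 0.

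If causality is asked for each drug, and the same share *q* is judged related to a drug given in that period, the expected count is 0.9 to 5.4 on both treatments and the gap disappears. If *q* = 0, there is no gap under the bexagliflozin-only rule, but no digoxin reaction is identified as drug-related under either treatment.

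**4. Definitions that bear on the same tables.**

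| Item | Protocol 9.6.1 | SAP |
|---|---|---|
| Treatment-emergent | on or after bexagliflozin | after either drug (6.3.3.1) |
| Related | at least possibly related to bexagliflozin | abbreviation TR also includes Not Likely |
| Missing relationship | no rule | counted as related (8.4.1) |

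On the Protocol wording, an event in Group 2 Period 1 is not even treatment-emergent; the SAP corrects that. The TR class could widen the asymmetry, because Not Likely needs only a temporal link to bexagliflozin, which daily dosing on Treatment A readily supplies.

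**The case against.** The strongest reply is that the quoted sentence does not settle the matter. *Study compound* is not defined, and the sample-size sections (Protocol 9.2, SAP 3.5) use *the compound* for digoxin. The SAP wording can be read as covering both drugs. This stands in part: the Protocol reading rests on Sections 5.1.1, 5.1.2 and 9.6.1 together with the grades, not on that sentence alone. But if both drugs were meant, the Protocol and SAP conflict and the wording still needs repair. SAP wording also cannot supply a digoxin judgement that sites were not asked to make.

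Second, SAP 8.4.1 names an overall summary of treatment-emergent events and two tables by system organ class and preferred term, one for all such events and one for serious ones. The latter two do not depend on causality. Related tables appear there only in the missing-data rule. This stands. A by-treatment related table is possible, since SAP 8.4 summarises all safety data by treatment, but it is not named. The CRF and table shells are separate documents not available here, so what is actually collected and displayed cannot be confirmed.

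Third, a reader might infer that every event on Treatment B must be graded Unrelated. The documents support this only for Group 2 Period 1. In Group 1 Period 2 late attribution is open, and the missing-relationship rule can place a Treatment B event in a related table.

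Fourth, a reader might infer that the secondary objective is itself biased. The documents do not support that: it is stated as the safety of digoxin when co-administered, not as a comparison of related events, and no test is planned. The direction is also uncertain, because an investigator asked about bexagliflozin may judge a digoxin reaction on Treatment A unrelated.

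**Conclusion.** The concern holds in limited form. The Protocol ties relatedness to bexagliflozin and describes no causality question for digoxin, the drug whose safety is the secondary objective. A digoxin reaction cannot be classed as related in about 9 digoxin-alone subject-periods, and is very unlikely to be in the other 9 or so, where bexagliflozin stopped 27 to 34 half-lives earlier. Any by-treatment display of related events could therefore mislead, most likely against the combination.

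The size, 0.9–5.4 of 18 on A against about 0 on B, is illustrative and rests wholly on the assumed event rates and attribution shares. The main all-causality and serious-event tables, and the primary pharmacokinetic analysis, are untouched. The SAP may intend both drugs, but it does not say so clearly enough to override the Protocol criteria it points to.

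**What to change.** In Protocol 6.7 and 9.6.1, the adverse-event CRF page and SAP 6.3.3.6, record causality separately for digoxin and for bexagliflozin. If only one field is possible, redefine it as relationship to any study drug given in that period. Tabulate, by treatment, treatment-emergent events at least possibly related to any study drug.

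In the same revision:

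- use one treatment-emergent definition in Protocol 9.6.1 and SAP 6.3.3.1;
- use one definition of related, settling whether Not Likely belongs in it (Protocol 9.6.1 against the SAP abbreviation TR);
- correct the cross-reference in SAP 6.3.3.6 from Protocol Section 6.9 to 6.7.

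The cost is one extra or reworded CRF field and some wording in the Protocol and SAP, with no added visits or tests. It is best done before data collection, because causality is best judged when the event occurs.
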